## **5.2 EXCLUSION CRITERIA**

Participants are excluded from the study if any of the following are met at screening and Day -1:

### **Medical Conditions**

1. Any condition or disease detected during the medical interview/physical examination that would render the participant unsuitable for the study, place the participant at undue risk or interfere with the ability of the participant to complete the study, as determined by the Investigator.
2. History or evidence of any medical condition potentially altering the absorption, metabolism or elimination of drugs. This includes a surgical history of the gastrointestinal tract affecting gastric motility or altering the gastrointestinal tract.
3. History or evidence of any medical condition that potentially may alter the taste sensory perception including ageusia and dysgeusia.
4. History of any clinically significant gastrointestinal, renal, hepatic, bronchopulmonary, neurological, psychiatric, cardiovascular, endocrinological, hematological or allergic disease, metabolic disorder, hypofertility, cancer or cirrhosis
5. Use of any psychoactive medication, or medications known to have effects on CNS or blood flow taken within 30 days prior to first dosing (or within 5 times the elimination half-life of the medication prior to first dosing, whichever is longer).
6. History of convulsions (other than benign febrile convulsions of childhood) including epilepsy, or personal history of significant cerebral trauma or CNS infections (e.g. meningitis).
7. A history of clinically significant hypersensitivity (e.g., drugs, excipients) or allergic reactions.
8. Any major illness within one month before the screening examination or any febrile illness within one week prior to screening and up to first study drug administration.
9. Abnormal blood pressure, defined as confirmed (based on the average of  $\geq 3$  consecutive measurements at screening and Day -1) systolic blood pressure (SBP) greater than 140 or less than 90 mm Hg, and diastolic blood pressure (DBP) greater than 90 or less than 50 mm Hg.
10. Abnormal pulse rate, defined as confirmed (based on the average of  $\geq 3$  consecutive measurements at screening and Day -1) resting pulse rate greater than 100 or less than 40 bpm.
11. History or presence of clinically significant ECG abnormalities before study drug administration (e.g. PQ/PR interval  $> 210$  ms, QTcF  $> 450$  ms) or cardiovascular disease (e.g. cardiac insufficiency, coronary artery disease, cardiomyopathy, congestive heart failure, family history of congenital long QT syndrome, family history of sudden death).
12. Clinically significant abnormalities in laboratory test results (including hepatic and renal panels, complete blood count, chemistry panel and urinalysis). In the case of

uncertain or questionable results, tests performed during screening may be repeated before randomization to confirm eligibility.

13. ALT and/or bilirubin  $> 1.5 \times \text{ULN}$  (isolated bilirubin  $> 1.5 \times \text{ULN}$  is acceptable if bilirubin is fractionated and direct bilirubin  $< 35\%$ ).
14. Current or chronic history of liver disease, or known hepatic or biliary abnormalities (with the exception of Gilbert's syndrome or asymptomatic gallstones).
15. Participants who, in the Investigator's judgment, pose a suicidal or homicidal risk, or any participant with a history of suicidal or homicidal attempts.

#### **Prior/Concomitant Therapy**

16. Have used or intend to use over-the-counter or prescription medication including herbal medications within 30 days prior to dosing. Specific medications listed in [Section 6.5.1](#) will be allowed.
17. Participants likely to need concomitant medication during the study period (including for dental conditions).

#### **Prior/Concurrent Clinical Study Experience**

18. Participation in an investigational drug or device study within 90 days prior to screening, as calculated from the day of follow-up from the previous study, or more than 4 participations in an investigational drug or device study within a year prior to dosing.

#### **Diagnostic Assessments**

19. Positive test for drugs of abuse or alcohol.
20. Show evidence of human immunodeficiency virus (HIV) infection and/or positive human HIV antibodies.
21. Presence of hepatitis B surface antigen (HBsAg) or positive hepatitis C antibody test result at screening or within 3 months prior to starting study treatment.

#### **Other Exclusions**

22. Dietary restrictions that would prohibit the consumption of standardized meals.
23. Consumption of any prohibited food and beverages before study start and during the study (see [Section 5.3](#)).
24. Inability or unwillingness to fully consume standardized breakfast at Day 1 (for Part 1, Treatment C only).
25. Any suspicion or history of alcohol abuse and/or suspicion of regular consumption of drug of abuse or previous history of or treatment for a dependence disorder.
26. Sensitivity to any of the study treatments, or components thereof, or drug or other allergy that, in the opinion of the Investigator, contraindicates the participation in the study.

27. Participants who have donated over 500 mL of blood or blood products or had significant blood loss within 3 months prior to screening.

### **5.3 LIFESTYLE CONSIDERATIONS**

#### **5.3.1 Meals and Dietary Restrictions**

Participants will have to be fasted for at least 4 hours prior to laboratory safety tests at screening and the follow-up visit, and for at least 8 hours prior to laboratory safety tests performed on Day -1 and Day 3.

Consumption of nutrients known to modulate CYP3A activity (e.g., grapefruit or grapefruit juice, Seville orange) will not be permitted within 2 weeks prior to first dosing until the safety follow up visit.

Please note that participants should refrain from consumption of any foods containing poppy seeds within 48 hours (2 days) prior to screening and each admission to the clinical unit to avoid false positive drug screen results.

#### **5.3.2 Caffeine, Alcohol, and Tobacco**

The consumption of food and beverages containing caffeine or other methylxanthine-containing products (e.g., tea, coffee, caffeinated soft drinks, cola, chocolate) will not be permitted from 48 hours before each dosing until the end of each residential period. During the period from screening to the follow-up visit when participants are not resident in the unit, participants will be asked to limit coffee or tea consumption to no more than 3 cups per day, and methylxanthine-containing products (e.g. cola and chocolate) must be limited to a maximum of 1 L per day.

Consumption of alcohol will not be allowed from 48 hours before each dosing until the end of each residential period and participants will be asked to limit alcohol to a maximum of 2 units/day (1 unit equates to approximately 330 mL beer, 125 mL of wine or 25 mL of spirits) during the out-clinic period until follow-up.

Smoking is not permitted. For inclusion into this study, participants must be non-smokers.

### **5.3.3 Activity**

Participants should refrain from strenuous exercise from at least 96 hours prior to each admission to the clinical research unit until discharge from the unit and from 96 hours prior to the follow-up visit. The level of activities should be kept as similar as possible on all study days until the follow-up visit.

In addition, any participants who experience severe drowsiness or somnolence during their in-clinic stay will be advised to limit driving or operating dangerous machinery in the 3 days after discharge.

### **5.4 SCREEN FAILURES**

Screen failures are defined as participants who consent to participate in the clinical study but are not subsequently randomized to study treatment/entered in the study.

The Investigator will maintain a screening log to record details of all participants screened and to confirm eligibility or record reasons for screening failure.

Individuals who do not meet the criteria for participation in this study (screen failure) will not be re-screened, unless agreed with the Sponsor. A repeat of a screening laboratory test because of uncertain or questionable results during screening is not considered a re-screening.

### **5.5 RECRUITMENT PROCEDURES**

Participants will be identified for potential recruitment using pre-screening enrollment logs, clinical database and IEC/IRB approved newspaper/radio/social-media advertisements prior to consenting to take place on this study.

## **6. TREATMENTS**

Study treatment is defined as any investigational treatment(s) intended to be administered to a study participant according to the study protocol.

All investigational medicinal products (IMPs) required for completion of this study (RO7017773 Phase I capsules and Phase II tablets) will be provided by the Sponsor. All study drug administration will be done at the study center under supervision of site staff.

### **6.1 TREATMENTS ADMINISTERED**

[Table 7](#) summarizes the treatments administered. Please see the Investigator's Brochure and Pharmacy Manual for more details.

**Table 7 Summary of Treatments Administered**

Study Treatment Name:	RO7017773 Phase I capsule	RO7017773 Phase II tablet without sweetener/flavor	RO7017773 Phase II tablet with sweetener/flavor
Dosage Formulation:	capsule	film-coated tablet	film-coated tablet
Dose/Dose Strength:	[REDACTED] mg		
Route of Administration:	oral		
Dosing Instructions:	Fasted Conditions: RO7017773 Phase I capsule will be administered in the morning after overnight fast with water.	Fasted Conditions: RO7017773 Phase II tablet will be administered in the morning after overnight fast with water. Fed Conditions: RO7017773 Phase II tablet will be administered [REDACTED] [REDACTED] Taste assessments: RO7017773 Phase II tablet will be administered in the morning after overnight fast dispersed in either water or apple juice.	Taste assessments: RO7017773 Phase II tablet with sweetener/flavor will be administered in the morning after over-night fast dispersed in water.
Packaging and Labeling:	Study treatment will be provided in bottles. The IMP will be labeled as required per country requirements		
Storage Conditions	Store at 2°C to 8°C, protect from light and moisture		
Manufacturer	F. Hoffmann-La Roche Ltd.		

## **6.2 PREPARATION/HANDLING/STORAGE/ACCOUNTABILITY**

Study drug packaging will be overseen by the Roche clinical trial supplies department and bear a label with the identification required by local law, the protocol number, drug identification and dosage.

The packaging and labeling of the study medication will be in accordance with Roche standard and local regulations.

The investigational site will acknowledge receipt of IMPs and confirm the shipment condition and content. Any damaged shipments will be replaced.

Upon arrival of the IMPs at the site, site personnel will complete the following:

- Check the IMPs for damage.
- Verify proper identity, quantity, integrity of seals and temperature conditions.
- Report any deviations or product complaints to the Monitor upon discovery.

The qualified individual responsible for dispensing the study treatment will prepare the correct dose according to the treatment assignment schedule.

The Investigator or delegate must confirm appropriate temperature conditions have been maintained during transit for all study treatment received and any discrepancies are reported and resolved before use of the study treatment.

Only participants enrolled in the study may receive study treatment and only authorized site staff may supply or administer study treatment. All study treatments must be stored in a secure, environmentally controlled, and monitored (manual or automated) area in accordance with the labeled storage conditions with access limited to the Investigator and authorized site staff.

The Investigator, Institution, or the Head of the Medical Institution (where applicable) is responsible for study treatment accountability, reconciliation, and record maintenance (i.e., receipt, reconciliation and final disposition records).

IMPs will either be disposed of at the study site according to the study site's institutional standard operating procedure (SOP) or returned to the Sponsor with the appropriate documentation. The site's method of IMP destruction must be agreed upon by the Sponsor. Local or institutional regulations may require immediate destruction of used IMP for safety reasons. The site must obtain written authorization from the Sponsor before any IMP is destroyed, and IMP destruction must be documented on the appropriate form.

Further guidance and information for the final disposition of unused study treatment are provided in the Pharmacy Manual.

## **6.3 MEASURES TO MINIMIZE BIAS: RANDOMIZATION AND BLINDING**

### **6.3.1 Method of Treatment Assignment**

Study is open-label. The randomization numbers will be generated by the Sponsor or its designee.

To minimize the carryover effects, a Williams Latin Square design is used to assign participants to four different sequences in Part 1 ([Table 1](#) and [Table 2](#) and two different sequences in Part 2 ([Table 3](#) and [Table 4](#)).

The randomization list will be made available to the Pharmacist preparing the study treatment (if necessary), to the individual responsible for PK sample bioanalysis (and PD bioanalysis, if appropriate) and to statisticians or programmers at Roche.

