#### 4.1.1 **Dosing regimen**

Following a screening period of up to 4 weeks participants will receive 4 (Part 1) or 2 (Part 2) single oral doses of RO7017773.

The following treatments will be administered in Part 1 (4 period crossover):

- Treatment A: Phase I capsule swallowed whole under fasted conditions
- Treatment B: Phase II tablet swallowed whole under fasted conditions
- Treatment C: Phase II tablet swallowed whole under fed conditions
- Treatment D: Phase II tablet dispersed in water under fasted conditions (taste assessment)

The following treatments will be administered in Part 2 (2 period crossover) in different participants to Part 1:

- Treatment A: Phase II tablet containing flavor and/or sweetener dispersed in water under fasted conditions (taste assessment)
- Treatment B: Phase II tablet without flavor and/or sweetener dispersed in apple juice under fasted conditions (taste assessment)

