### **6.3.2 Blinding**

This is an open-label study, blinding procedures are not applicable.

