## **8.5 PHARMACOKINETICS**

Blood samples for the determination of plasma concentrations of RO7017773 will be collected as outlined in the SoA (see [Section 1.3](#)). Plasma RO7017773 concentrations will be measured by a specific and validated LC-MS/MS method. Plasma concentrations of RO7017773 metabolites may also be measured as appropriate using a specific assay.

PK parameters for RO7017773 (and its metabolite, as appropriate) will be read directly from the plasma concentration-time profiles or estimated using standard non-compartmental methods where appropriate.

Any volume of blood samples remaining after the specified analyses may also be used for additional validation experiments specify for, e.g., metabolites and exploratory biomarkers.

The plasma samples will be destroyed up to 2 years after the date of final clinical study report (CSR). Details on sampling procedures, sample storage and shipment are given in the Sample Handling Manual.

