## **8.6 PHARMACODYNAMICS**

Pharmacodynamic parameters are not evaluated in this study.

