## **8.8 BIOMARKERS**

Biomarkers are not evaluated in this study.

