**Table 8 Analysis Populations**

Population	Description
Safety	All participants randomized to study treatment and who received at least one dose of the study treatment, whether prematurely withdrawn from the study or not, will be included in the safety analysis.
Pharmacokinetic	All participants who have received at least one dose of study treatment and who have data from at least one post-dose sample will be included in the PK analysis population. Participants will be excluded from the PK analysis population if they significantly violate the inclusion or exclusion criteria, deviate significantly from the protocol, or if data are unavailable or incomplete which may influence the PK analysis. Excluded cases will be documented together with the reason for exclusion. All decisions on exclusions from the analysis will be made prior to database closure.

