16.1.1 Plasma Pharmacokinetic Parameters

The following plasma PK parameters for RO7017773 and metabolites will be estimated.

Parameter	Description
Tmax	Time to maximum plasma concentration. First observed time to reach peak analyte concentration obtained directly from the experimental data without interpolation, expressed in time units.
Cmax	Maximum plasma concentration. Observed peak analyte concentration obtained directly from the experimental data without interpolation, expressed in concentration units
AUC0-t	Area under the plasma concentration-time curve from time 0 to t hours post-dose.
AUClast	Area under the plasma concentration-time curve (time 0 to time of last quantifiable concentration).
AUCinf	Area under the plasma concentration-time curve (time 0 to infinity). Percent extrapolation less than or equal to 20% is required to obtain a reliable AUCinf.
T1/2	Apparent terminal half-life, calculated as $\ln(2)/\lambda z$
CL/F	Apparent oral clearance, calculated as Dose/AUCinf

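### The bioanalyst is given the randomization list with no stated need or release time, although every treatment contains RO7017773 and no PD is evaluated; withholding it until concentrations are final is a cheap improvement.

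*Protocol*

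**What the plan says.** Protocol Section 6.3, on measures to minimize bias, names who may see the randomization list. Section 6.3.1 gives it to the pharmacist if necessary, and then "to the individual responsible for PK sample bioanalysis (and PD bioanalysis, if appropriate) and to statisticians or programmers at Roche". No purpose is given for the bioanalyst's access, and no point in time for release. SAP Section 6.2 says who generates the schemes but nothing about access to them.

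Section 6.3.2 sets masking aside altogether: "This is an open-label study, blinding procedures are not applicable".

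Other sections bear on whether the access is needed:

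- Section 4.1.1: "participants will receive 4 (Part 1) or 2 (Part 2) single oral doses of RO7017773". Neither part has a placebo or another drug as comparator.
- Section 8.6: "Pharmacodynamic parameters are not evaluated in this study". Section 8.8: "Biomarkers are not evaluated in this study".
- Section 8.5: "Plasma RO7017773 concentrations will be measured by a specific and validated LC-MS/MS method".

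Later steps also involve judgement. Table 8 allows participants to be excluded from the PK population for significant violations or incomplete data, and adds: "All decisions on exclusions from the analysis will be made prior to database closure". SAP Section 16.1.1 sets an acceptance limit for AUCinf: "Percent extrapolation less than or equal to 20% is required to obtain a reliable AUCinf". Neither document asks for masking at these steps.

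**The concern.** Open-label dosing means that participants and site staff know the treatment. It does not mean that the laboratory must. Sample measurement can be kept masked in an open-label crossover by not passing on the sequence, and this plan instead provides for the sequence to be passed on.

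The Part 1 primary comparison is the geometric mean ratio of A and B for AUC and Cmax, with a 90% confidence interval (Protocol Section 9.5). Those variables come entirely from the measured concentrations. If the analyst holds the list during the assay, choices such as repeating a sample, re-integrating a peak or accepting an odd value could be made knowing whether it came from the capsule or the tablet. That is a possible route for handling A and B samples differently, and the plan gains nothing that it names in return.

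**Working it through.** No figure in the plan depends on this point: sample size, confidence level and model are the same whether or not the bioanalyst holds the list. The check is therefore mainly a comparison of sections.

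**Is a need for the list stated or implied?**

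1. Separating samples with drug from samples without. All four Part 1 treatments and both Part 2 treatments contain RO7017773 (Protocol Section 4.1.1 and Table 7). Pre-dose samples are identified by sampling time, not by treatment. The list is not needed for this.
2. PD bioanalysis. The entry is conditional, and with no PD evaluated (Section 8.6) the condition is never met.
3. Exploratory metabolite work. Sections 4.2.2 and 8.5 allow metabolite screening and retrospective measurement in residual plasma. If treatment identity helps there, it can be supplied after the parent-drug concentrations are final.
4. Planning dilutions by treatment. This is a possible convenience, though the documents do not mention it.

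**Is there a natural release point?** Yes. SAP Section 8.2 uses only quality-assured results released by the bioanalytical laboratory. Assignments can be withheld until that release without delaying the analysis.

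**Which other stages could be masked?** Non-compartmental estimation (SAP Section 16.1), acceptance of AUCinf (SAP Section 16.1.1) and PK-set exclusions (Protocol Table 8, SAP Section 10.2). An exclusion can remove a whole participant from the A vs B comparison, so it matters at least as much as a single repeat assay.

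**Scale, by illustration only.** The bias itself cannot be computed. Assume that one participant's Cmax under one treatment is changed by 20% (an assumption, not a figure from the documents). Take complete data balanced over the four sequences. The model estimate of ln(A/B) is then the mean of the n within-participant differences, so the ratio is multiplied by exp(ln(1 + change)/n). The values n = 12 (evaluable) and n = 16 (enrolled) come from Protocol Section 9.2.

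| Change in one A value | n = 12 | n = 16 |
|---|---|---|
| +20% | exp(0.1823/12) = 1.015 | exp(0.1823/16) = 1.011 |
| −20% | exp(−0.2231/12) = 0.982 | exp(−0.2231/16) = 0.986 |

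The ratio moves by 1.1% to 1.8%. A change to a B value moves it by the reciprocal factor. With missing periods or unbalanced sequences the figures are approximate.

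**The case against.** The strongest reply is that nothing here is shown to go wrong. The study is declared open-label. The assay is instrument-based and validated. Neither document describes treatment-aware re-integration, re-assay or rejection. Making a list available does not say that the analyst holds it while running samples. Sampling and shipment details are in a Sample Handling Manual that is not among the documents. No hypothesis is tested, and the sample-size criteria are explicitly not strict bioequivalence criteria, so a shift of one or two percent changes no visible decision. All of this stands, and it keeps the point minor.

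Three further objections limit what may be claimed:

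- A reader might infer that bioanalysis is the only stage left to mask. It is not; the later steps named above could be masked too.
- The sentence in Section 6.3.1 also gives the list to statisticians or programmers at Roche, and SAP Section 3.0 has Roche process the PK results. Removing the bioanalyst alone leaves those steps unmasked. These staff do need treatment codes for summaries by treatment, so removing them is not proposed.
- The PD entry is surplus conditional wording. It is worth deleting, but nobody receives the list under it.

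None of this shows a need for the bioanalyst to have the list before results are final. The two candidate uses, dilution planning and metabolite work, are respectively a small convenience and something that can wait.

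**Conclusion.** The point holds as a minor design improvement. The plan states a rule that gives the bioanalyst the treatment list, with no reason and no timing, in a study where the obvious reasons for access are absent. Laboratory decisions could therefore be made knowing the treatment.

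The documents do not support the stronger readings that laboratory decisions will be treatment-aware or that the A vs B ratio is biased. Any bias is probably small, and its size cannot be estimated. The shift of 1.1% to 1.8% shows only how far one altered value would move the ratio; it rests on an assumed 20% change and complete, balanced data. Nor would masking the laboratory be entirely free.

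The conclusion also assumes that sample labels and shipping lists do not themselves show the treatment. The documents do not settle this.

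**What to change.** In Protocol Section 6.3.1, remove the individual responsible for PK bioanalysis and the bracketed PD reference from the recipients of the list, and add:

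*The bioanalytical laboratory will not receive treatment assignments until the RO7017773 concentration data are final.*

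Carry the same instruction into the laboratory documents, including what sample labels may show.

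Where feasible, also state in Table 8 and SAP Section 10.2 that PK-set exclusions will be decided without knowledge of treatment. This will not always be possible: a deviation concerning the test meal, for example, reveals Treatment C.

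The cost is a sentence in the protocol, matching laboratory instructions and, if adopted, the line on exclusions. The laboratory loses the option of planning dilutions by treatment, and exploratory metabolite work that needs treatment identity waits until release. Sample size, model and clinical procedures do not change.
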